2. STUDY OBJECTIVES

2.1. Objectives

Primary Objective:

- To evaluate the time-to treatment discontinuation (TTD) of lorlatinib with locally therapy in unresectable ALK-positive NSCLC patients who have received 1L lorlatinib in real-world settings;

Secondary Objectives:

- To evaluate the rwORR, rwDCR and real-world intracranial ORR, intracranial time to progression (IC-TTP) and TTP of 1L lorlatinib in real world setting ;
 - To explore the progression pattern in this therapeutic changing mode;
- To evaluate 1/2/3/4/5-year overall survival (OS) rate and OS of in each treatment cohort;
- To explore the association between the effectiveness of lorlatinib in first line for Chinese patients with ALK-positive locally advanced or metastatic NSCLC patients with baseline brain metastases (Yes or No) , ALK Fusion Variants ([V1, V2, V3] and

TP53 mutation status [TP53 mutation, TP53 WT]) if data is available in medical records;

- To evaluate the safety and tolerability of the therapeutic changing mode;
 - To explore the adverse events (AEs), the dose modification and the reason for interruption or discontinuation of lorlatinib in first line for Chinese ALK-positive locally advanced or metastatic NSCLC recorded in medical records;
 - To evaluate patient-reported outcomes (PROs) of health-related quality of life for this therapeutic mode;
 - To describe the demographic, clinicopathological and baseline co-mutation characteristics of enrolled patients.

Exploratory Objectives:

- To explore dynamic ctDNA change during lorlatinib treatment;
- To evaluate candidate biomarkers of sensitivity or resistance to lorlatinib in no-prior ALK-TKIs treatment tumor tissue and peripheral blood if available in real world setting;

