lorlatinib enrolled in this study, follow-up visits are performed by investigator to collect study-related data, including data on effectiveness, tumor status, and other study required variables. A final data collection will be performed at death, withdrawal of consent, loss to follow-up, or the end of the study which is the earliest occurrence. There is no fixed visit schedule; visits will follow local routine clinical practice. Data will be collected until the 60th month after patient enrolled in this study (last follow-up time) or the death of patients due to any cause, loss to follow-up or withdrawal from the study which is the earliest occurrence.

Data type:

The clinical data collected for this study include, but is not limited to:

Collect patients' baseline demographic information (including age at diagnosis, gender, height, weight, physical examination, smoking status), ECOG score, past history, baseline disease characteristics (disease stage, molecular typing, pathological diagnosis), laboratory test results (blood routine, urine routine, blood biochemistry, coagulation function tests, electrocardiogram, echocardiography, vital signs), ALK genetic testing methods and results, test specimen types, imaging tests (tumor assessment[size, number, and location], medication treatment, adverse events, post-resistance gene testing, dose modification regimens, reasons for lorlatinib dose modification, interruption or discontinuation, PRO (if data is available in clinical practice) and survival status.

Collection and recording of SAEs and AEs will commence once the study participant has provided informed consent and terminate till 28 (and no more than 35) days after administration of the last dose of lorlatinib. After this period, only lorlatinib-related SAEs must be reported to the Pfizer. SAEs should be monitored until they are resolved or are clearly determined to be due to a patient's stable or chronic condition or intercurrent illness(es). All patients will be periodically contacted for survival and safety information unless the patient requests to be withdrawn from the study. Survival status is also encouraged to be confirmed through a telephone follow-up by the investigator or designee at the end of the study or withdrawal from the study.

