4.1 Inclusion Criteria

Subjects must meet all of the following inclusion criteria to be eligible for enrollment into the study:

1. Diagnosis:

- a. Study Population: Patients with histologically or cytologically confirmed diagnosis of locally advanced [(Stage IIIB/C not amenable for multimodality treatment) or metastatic (Stage IV) by American Joint Committee on Cancer (AJCC) v 7.0] ALK-positive NSCLC where ALK status is determined by the Ventana ALK (D5F3) Companion Diagnostic (CDx) IHC test performed on the Ventana ULTRA or XT Platforms, FISH, PCR, or next generation sequencing (NGS), or circulating tumor DNA (ctDNA).

- b. Tumor Requirements: At least 1 measurable target lesion per RECIST v. 1.1 that has not been previously irradiated. Brain metastases are allowed.
 2. No prior systemic treatment for advanced (Stage IIIB/C not amenable for multimodality treatment) or metastatic (Stage IV) disease.
 3. Eastern Cooperative Oncology Group Performance Status (ECOG PS) 0, 1, 2 or 3.
 4. Age ≥ 18 years.
 5. Adequate Liver Function, including:
 - a. Total serum bilirubin ≤ 1.5 x ULN;
 - b. Aspartate Aminotransferase (AST) and Alanine Aminotransferase (ALT) ≤ 2.5 x ULN (≤ 5.0 x ULN in case of liver metastases).
 6. Life expectancy at least 6 months.
 7. Serum pregnancy test (for females of childbearing potential) negative at screening. Female patients of non-childbearing potential must meet at least 1 of the following criteria:
 - a. Achieved postmenopausal status, defined as follows: cessation of regular menses for at least 12 consecutive months with no alternative pathological or physiological cause (which may be confirmed with a serum follicle-stimulating hormone [FSH] level confirming the postmenopausal state if appropriate);
 - b. Have undergone a documented hysterectomy and/or bilateral oophorectomy;
 - c. Have medically confirmed ovarian failure.
- All other female patients (including female patients with tubal ligations) are considered to be of childbearing potential.

8. Evidence of a personally signed and dated informed consent document indicating that the patient (or a legally acceptable representative) has been informed of all pertinent aspects of the study.

9. Willing and able to comply with scheduled visits, treatment plans, laboratory tests and other procedures.

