9.2.5 Analysis of Secondary Endpoints

rwPFS, IC-TTP and Overall Survival will be summarized using Kaplan-Meier methods and displayed graphically. The 1/2/3/4/5-year rwPFS, IC-TTP and survival probability will be estimated using Kaplan-Meier methods and the 2-sided 95% CI will be provided. Potential influences of other demographic, baseline characteristics including biomarker profile use parametrical test, χ^2 or Fisher exact test. Objective Response Rate will be summarized for the SAT Population based on the investigator's assessment. The number and percent of subjects achieving objective response (CR or PR) will be summarized along with corresponding 2-sided 95% CI using the binomial distribution.

Intracranial Objective Response Rate will be summarized for the SAT Population based on the investigator's assessment. The assessment of intracranial response will be conducted on subjects with measurable and unmeasurable CNS metastases. The number and percent of subjects achieving objective response (CR or PR) will be summarized along with corresponding 2-sided 95% CI using the binomial distribution.

Subgroup analysis is considered to be conducted by baseline characteristics such as CNS (Yes/No), TP53 status (Yes/No), ALK-EML4 fusion variant (V1, V2, V3) in patients with baseline who receive lorlatinib in first line. Depending on the actual sample size at the time of analysis, adjustment by either combining or re-classifying the subgroups will be applied as needed.

Subgroup comparisons, where is applicable, will be performed using the Kaplan-Meier method and the log-rank test. Statistically significant level of $\alpha=0.05$ (two sides) is used for tests.

The qualitative exploratory endpoints will be categorized and summarized descriptively by count and percentage of patients. Missing data will be categorized by missing, unknown, or can't be determined.

The interim analysis will be performed when the completion of 2.5 year follow-up in late patient. The final full analysis will take place at the time of data cut-off (i.e. the completion of 60-month follow-up for all the participants).

Descriptive statistics will be used to summarize subject characteristics, study conduct, subject disposition, treatment administration/compliance, and safety parameters. Data will also be displayed graphically, where appropriate.

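### The brain-metastasis Yes/No comparison pools Stage IIIB/C with Stage IV, so it partly measures stage; make the comparison among Stage IV patients the main one (minor)

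*Protocol*

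**What the plan says.** - **Objective (Protocol 2.1).** One secondary objective explores the association of first-line effectiveness with several baseline factors, in a population that spans both stages: "for Chinese patients with ALK-positive locally advanced or metastatic NSCLC patients with baseline brain metastases (Yes or No"). ALK fusion variant and TP53 status are the other factors named.
- **Population (Protocol 4.1, criterion 1).** Eligible disease is "locally advanced [(Stage IIIB/C not amenable for multimodality treatment) or metastatic (Stage IV) by American Joint Committee on Cancer (AJCC) v 7.0"]. The same criterion adds that "Brain metastases are allowed".
- **Grouping (Protocol 9.2.5).** "Subgroup analysis is considered to be conducted by baseline characteristics such as CNS (Yes/No), TP53 status (Yes/No), ALK-EML4 fusion variant (V1, V2, V3"). Stage is not among the examples.
- **Test (Protocol 9.2.5).** "Subgroup comparisons, where is applicable, will be performed using the Kaplan-Meier method and the log-rank test", at a two-sided level of 0.05. No strata, covariates or restriction to Stage IV are stated. The only adjustment mentioned is merging or re-classifying subgroups.
- **Data (Protocol 3.1, Data type).** Stage is collected: "baseline disease characteristics (disease stage, molecular typing, pathological diagnosis").
- **Status of the analysis (Protocol 10.2, limitations text).** The study is called descriptive, with no hypothesis testing. That sits uneasily with the significance level in 9.2.5.

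**The concern.** The protocol's own labels equate Stage IIIB/C with locally advanced disease and Stage IV with metastatic disease. A patient with brain metastases is therefore Stage IV, and every IIIB/C patient is in the No group. The Yes group is purely Stage IV, while the No group is a mixture. A difference between the two curves can then reflect stage alone, even if brain metastases make no difference among Stage IV patients.

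The Introduction gives lorlatinib's intracranial activity as a main reason for the study, so readers will look at this contrast. Enrolling more patients would narrow the confidence interval without removing the mixing.

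**Working it through.** **No plan figure to reproduce.** Protocol 9.1 says that the sample size of about 100 does not rest on statistical assumptions. No effect size, event count or power is given for this comparison.

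**Step 1: structure**

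| | Brain metastases: Yes | Brain metastases: No |
|---|---|---|
| Stage IIIB/C | none, by definition | all |
| Stage IV | all with brain metastases | the rest |

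**Step 2: inputs for the size**
- Share with brain metastases: 37/149 = 0.248, from the lorlatinib arm of the phase 3 trial described in the Introduction. Carrying it over to this study is an assumption.
- IIIB/C share of all patients, s: 5%, 15% or 25% (assumed; not in the documents).
- IIIB/C event hazard relative to Stage IV, h: 0.5 to 0.8 (assumed; not in the documents).
- Effect of brain metastases within Stage IV: none, so that any apparent effect is due to stage.

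**Step 3: apparent hazard ratio**

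The IIIB/C fraction of the No group is f = s/(1 − 0.248). The average hazard in that group, relative to Stage IV, is f·h + (1 − f). Hence HR(Yes/No) = 1/(f·h + 1 − f).

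| s | f | HR at h = 0.8 | HR at h = 0.5 |
|---|---|---|---|
| 5% | 0.066 | 1.013 | 1.034 |
| 15% | 0.199 | 1.042 | 1.111 |
| 25% | 0.332 | 1.071 | 1.199 |

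This is the ratio at the start of follow-up. It drifts upward as the No group becomes richer in lower-hazard patients. Take the 63.5% progression-free rate at 36 months in the Introduction as the Stage IV rate (assumed). The monthly hazard is −ln(0.635)/36 = 0.0126, and Stage IV event-free survival at 60 months is 0.469. In the worst corner (s = 25%, h = 0.5), IIIB/C survival is 0.469^0.5 = 0.685. Then f becomes 0.332×0.685/(0.332×0.685 + 0.668×0.469) = 0.42, and the ratio is 1/(1 − 0.21) = 1.27 by month 60.

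**Step 4: comparison with sampling error**

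With that hazard, 60 months of follow-up and 20% loss (9.1 allows for at least 20%), about 45 events are expected in 100 patients. SE(log HR) ≈ 1/√(45 × 0.248 × 0.752) = 0.345, so a 95% interval runs about a factor of 2 either way, since exp(1.96 × 0.345) = 1.97. An apparent ratio of 1.11 is ln(1.11)/0.345 = 0.3 SE from no effect, and 1.20 is 0.5 SE.

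**Step 5: simulation**

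The setting was 100 patients, 4,000 runs per case and no true effect within Stage IV. At a 20% share, the pooled log-rank gave an apparent HR of 1.12 (h = 0.7) to 1.22 (h = 0.5), with rejection in 6.1% to 9.6% of runs at nominal 5%. At a 10% share and the same h, the HR was 1.06 to 1.11 and rejection about 5%. The Stage IV-only log-rank, over all shares from 5% to 30% and h from 0.3 to 0.7, gave an HR of 1.01–1.02 and rejection in 4.0% to 5.9%. So 0.01–0.02 of each simulated HR comes from the estimator itself.

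**Step 6: what the restriction loses**

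In a stage-stratified log-rank, the IIIB/C stratum has no Yes patients. Its expected Yes events and its variance are both zero, so it contributes nothing, and stratifying by stage gives the same test as restricting to Stage IV. Precision barely changes. At s = 25% and h = 0.5, about 43 events are expected in all and 36 in Stage IV, where the Yes share is 0.248/0.75 = 0.331. The SE is 1/√(43 × 0.248 × 0.752) = 0.353 pooled and 1/√(36 × 0.331 × 0.669) = 0.354 in Stage IV.

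**The case against.** The strongest reply is that 9.2.5 is deliberately open. Its subgroup factors are examples, its comparisons are conditional, and part of the sentence defining the subgroup population is missing. A statistical analysis plan, which is not at hand, could restrict or stratify by stage. The objective only explores an association, the limitations text in 10.2 calls the work descriptive, and a crude Yes/No contrast is a legitimate prognostic summary. The distortion is also small next to the sampling error.

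The points on size and exploratory status stand, and they set the severity. They do not remove the point. The protocol does state the pooled population, the grouping, the test and the level, and those choices together mix stage into the contrast. A descriptive curve carries the same mixing as a test.

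Two stronger readings are tempting, and the documents support neither:
- **That the comparison must always come out worse for patients with brain metastases.** This needs a lower event hazard in IIIB/C than in Stage IV, and the documents give no such figure. These IIIB/C patients are not amenable to multimodality treatment and take the same drug. Time to treatment discontinuation also counts stopping for reasons that need not follow stage.
- **That ECOG adjustment and multi-covariate Cox models for ALK variant and TP53 are needed.** No ECOG imbalance is documented. Poor performance status may itself result from brain metastases, so adjusting for it could remove part of the association under study. A three-level variant factor with stage and brain metastases already takes 2 + 1 + 1 = 4 parameters against some 45 events, and fewer would be usable because variant and TP53 are recorded only where available.

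**Conclusion.** The point holds as a minor one. That every IIIB/C patient falls in the No group is certain from the protocol's own stage labels. That this biases the result toward worse outcomes with brain metastases is conditional on IIIB/C patients having the lower event hazard.

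Under that assumption, with h from 0.5 to 0.8 and 24.8% of patients having brain metastases, the apparent hazard ratio with no true effect is about 1.01–1.03 at a 5% IIIB/C share, 1.04–1.11 at 15% and 1.07–1.20 at 25%, somewhat higher late in follow-up. At about 100 patients that is at most around half a standard error on the starting ratio. It would matter mainly if the IIIB/C share reached about 20% or more. The primary analysis is not affected.

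**What to change.** In 9.2.5, state that the main comparison by baseline brain metastases is made among Stage IV patients (equivalently, by a log-rank test stratified by stage) and is reported as a hazard ratio with 95% CI. Keep the pooled Yes/No Kaplan-Meier curves as a supplementary descriptive display, and show the number of IIIB/C patients in the No group beside them.

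The cost is a sentence of protocol or analysis-plan wording, with no new data because stage is already collected. The downside is that locally advanced patients drop out of this one comparison, though they carry no within-stage information on brain metastases.

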2.2. Endpoints

Primary Endpoint:

- Time-to treatment discontinuation (TTD) is defined as the time from start of treatment to the date of discontinuation of these therapeutic methods.

Secondary Endpoints:

- Effectiveness: Objective Response Rate (ORR), duration of response (DOR) and TTP based on investigator's assessment; intracranial ORR (IC-ORR), IC-time to progression (IC-TTP), progression pattern ,1/2/3/4/5-year rwOS rate and OS;
- Safety: To explore the adverse events (AEs), the dose modification and the reason

for interruption or discontinuation of lorlatinib in first line for Chinese patients with ALK-positive locally advanced or metastatic NSCLC recorded in medical records;

[figure not shown]
- Adverse Events (AEs), as graded by NCI CTCAE (National cancer Institute Common Terminology Criteria for Adverse Events) v5.0; laboratory abnormalities (as graded by NCI CTCAE v5.0); vital signs (blood pressure, pulse rate) and body weight; electrocardiograms (ECGs); echocardiogram or MUGA (multigated acquisition) scan; ophthalmologic data;
- PRO as assessed by EORTC (European Organization for Research and Treatment of Cancer) QLC-C30;
- To describe the demographic, clinicopathological and baseline co-mutation characteristics of enrolled patients.

Exploratory Endpoints:

- Dynamic molecular response associated with lorlatinib treatment using ctDNA as measured by next-generation sequencing (NGS) if available in real world setting ;
- Biomarkers of sensitivity or resistance to lorlatinib in no-prior ALK-TKIs treatment tumor tissue and peripheral blood if available in real world setting;

3. STUDY DESIGN

Figure 1. Study Design

3.1 Study design

This is a prospective, observational, multi-center, parallel-group, real world study to explore therapeutic changing mode of locally therapy after 1L lorlatinib treatment in unresectable ALK-positive Non-Small Cell Lung Cancer (NSCLC). Patients with unresectable NSCLC must have no previous systemic treatment for advanced (Stage IIIB/C not amenable for multimodality treatment) or metastatic (Stage IV) disease. All subjects must have tumors that test, positive for ALK rearrangement, with methods of Ventana ALK (D5F3), fluorescence in situ hybridization (FISH), polymerase chain reaction (PCR), or next generation sequencing (NGS), or circulating tumor DNA (ctDNA) for ALK rearrangement, with method of NGS. All tumors will be of histo- and/or cytopathology consistent with NSCLC, (e.g., adenocarcinoma, Squamous-cell carcinoma, or mixed), or its pathologically accepted variants.

The study will collect and analyze effectiveness, safety, PRO of lorlatinib in first-line from approximately 100 ALK positive locally advanced or metastatic NSCLC patients from study beginning to last subject last visit across approximately 8 sites in the real-world setting in China.

Lorlatinib will be administered orally QD at approximately the same time of the day on a continuous daily dosing schedule, ie, without a break in dosing in the absence of drug-related toxicity. Patients must swallow the study medication whole and must not manipulate or chew the medication prior to swallowing. A dosing card will be provided to the patients to provide guidance for the correct use of lorlatinib. Patients must be instructed that should they miss a dose or vomit any time after taking a dose, they must not “make it up” with an extra dose. Instead, resume the subsequent doses as originally prescribed. Any missed dose may be taken up to 6 hours prior to the next scheduled dose, otherwise it should be skipped and dosing resumed with subsequent doses as prescribed. The patient must be instructed to record all doses (including missed or vomited) in a dosing diary supplied by the site. If doses are missed or vomited, this must be indicated in the source documents and Case Record Forms (CRFs).

After lorlatinib treatment for 4 weeks, patients will receive an imaging assess. The patients who achieve PR or SD with oligometastasis (refer to target lesions with residual disease, a maximum of 3 organs, and no more than 5 lesions in total) should continue lorlatinib treatment and will receive imaging assess per 8-12 weeks. If target lesions indicate stable in 2 consecutive imaging, investigators will organize MDT and comprehensively evaluate patients' will to decide and choose local therapy. The local therapy includes surgery, ablation and, radiotherapy et al. After local therapy, patients should continue taking lorlatinib. While those who achieve CR or with multiple metastasis will continue lorlatinib treatment without any local therapy.

To dynamically monitor ctDNA changes in ALK + NSCLC patients during Lorlatinib treatment; to explore the correlation between ctDNA and Lorlatinib treatment efficacy .Patients need check the ctDNA-seq (10000x) in plamsa with NGS at baseline,4weeks after lorlatinib treatment and at disease progression.

Subjects will be on lorlatinib therapy until disease progression or unacceptable toxicity, new systemic anticancer therapy instituted, withdrawal of consent, death, or investigator decision dictated by protocol compliance, whichever occurs first.

Patients received continuous daily PO dosing of lorlatinib 100mg QD with/without locally therapy, from the date of first dosing (per the current protocol) or until one of the following criteria were met (whichever occurred first): disease progression; initiation of a new anti-cancer therapy; unacceptable toxicities; global deterioration of health-related symptoms; pregnancy; withdrawal of consent; loss to follow-up; death; investigator decision dictated by protocol non-compliance; or study termination. Patients who have progressive disease (PD) (per RECIST v1.1, by investigator review) and for whom the investigator believes it is in their best interest to continue lorlatinib treatment are allowed to continue lorlatinib therapy, at the discretion of the investigator, until any alternate or additional systemic anti-cancer therapy regimen was implemented.

At the time of progression and termination of study treatment, the patients could receive

any therapy at the judgment of the investigator. This study will take 1 years to enroll subjects, and each subject will be followed up for survival status and subsequent cancer therapies up to 60 months from the date of first dosing.

Participation in this study is not intended to change the routine treatment received as determined by their attending physicians. Patients will be treated according to the routine medical practice in terms of visit frequency and types of assessments performed.

Upon site initiation, investigators will consecutively enroll eligible patients into this study after obtaining patients' informed consent. The observation period for each patient is planned to be 60 months, starting from the patients who received lorlatinib enrolled in this study and ending at the earliest occurrence of the completion of 60 months of follow-up, death, loss to follow-up, or withdrawal from the study. The study data will be generated from the attending physician's routine clinical assessment during standard care. The data source used for data collection will be from electronic medical records/medical records or medical charts or other approved data source.

The study duration will be approximately 6 years. The enrollment period is planned to be about 12 months (from first site initiation, until the planned number of patients reached). The follow-up period per patient is up to 60 months from the time patients who received lorlatinib enrolled in this study. The interim analysis will be performed when half TTD events happen. The study is expected to be closed in about Oct 2030.

Safety and effectiveness assessments were performed throughout the treatment period and at the end-of-study visit. Routine safety assessments included the collection and evaluation of AEs, concomitant medications, vital signs, and body weight. Particular attention was given to AEs consistent with the lorlatinib toxicity profile (including lipid elevation, cognitive and mood disorder, etc.). Additional safety assessments performed at selected visits included ECOG PS, clinical laboratory tests, ECGs, and LVEF imaging. Contrast-enhanced computed tomography (CT) or magnetic resonance imaging (MRI) was used for tumor assessment at screening, at baseline, 4 weeks after lorlatinib treatment and then every 8-12 weeks. For patients with brain metastases,

RANO-BM criteria was used for intracranial lesions. Gadolinium-enhanced brain MRI is recommended at baseline and 4 weeks after lorlatinib treatment.

A post-treatment follow-up visit for safety occurred at least 28 days, and no more than 35 days, after discontinuation of treatment. All patients (regardless of the reason for discontinuation from study treatment) were to be followed for subsequent anti-cancer systemic therapies and survival status approximately every 6 months from the post-treatment follow-up visit, for up to 60 months from the date of first dosing (per the current protocol). Patients with no evidence of disease progression at the time of permanent treatment discontinuation were to be followed until disease progression; for these patients, repeat tumor assessments were suggested to occur approximately every 8-12 weeks from the date of the CT/MRI at the end-of-study treatment.

Subjects should be instructed to take their medication at approximately the same time every day.

Throughout the study, there was no fixed schedule of visits and safety assessments and effectiveness assessments will follow local clinical routine.

Data Source/Data Collection:

Data will be collected from approximately 8 hospitals. The data is sourced from the hospital information system (HIS)/electronic medical record (EMR)/laboratory information system (LIS)/ picture archiving and communication system (PACS), and genetic testing report data. All data collection will be done using LinkDoc data management platform. All data are based on medical records or genetic testing reports if available. The investigators at the sites are responsible for ensuring that the required data is collected and entered into the LinkDoc data management platform.

For each patient, the attending physician will document the clinical information during the initial visit, follow-up visits, and the final visit. The attending physician will document the baseline data (demographic and baseline disease characteristics) from medical records or through an interview at an initial visit. When patients who received

lorlatinib enrolled in this study, follow-up visits are performed by investigator to collect study-related data, including data on effectiveness, tumor status, and other study required variables. A final data collection will be performed at death, withdrawal of consent, loss to follow-up, or the end of the study which is the earliest occurrence. There is no fixed visit schedule; visits will follow local routine clinical practice. Data will be collected until the 60th month after patient enrolled in this study (last follow-up time) or the death of patients due to any cause, loss to follow-up or withdrawal from the study which is the earliest occurrence.

Data type:

The clinical data collected for this study include, but is not limited to:

Collect patients' baseline demographic information (including age at diagnosis, gender, height, weight, physical examination, smoking status), ECOG score, past history, baseline disease characteristics (disease stage, molecular typing, pathological diagnosis), laboratory test results (blood routine, urine routine, blood biochemistry, coagulation function tests, electrocardiogram, echocardiography, vital signs), ALK genetic testing methods and results, test specimen types, imaging tests (tumor assessment[size, number, and location], medication treatment, adverse events, post-resistance gene testing, dose modification regimens, reasons for lorlatinib dose modification, interruption or discontinuation, PRO (if data is available in clinical practice) and survival status.

Collection and recording of SAEs and AEs will commence once the study participant has provided informed consent and terminate till 28 (and no more than 35) days after administration of the last dose of lorlatinib. After this period, only lorlatinib-related SAEs must be reported to the Pfizer. SAEs should be monitored until they are resolved or are clearly determined to be due to a patient's stable or chronic condition or intercurrent illness(es). All patients will be periodically contacted for survival and safety information unless the patient requests to be withdrawn from the study. Survival status is also encouraged to be confirmed through a telephone follow-up by the investigator or designee at the end of the study or withdrawal from the study.

